3.4 Treatment at Primary Institution

All experimental protocol therapy should be dispensed and all on treatment imaging studies should be obtained at the primary PBTC institution. Laboratory studies, excluding pharmacokinetic and biologic assays, may be performed at a CLIA certified laboratory of the investigator's choice.

Imaging utilized to determine eligibility may be performed at an outside institution if all required imaging sequences are included and the study is deemed of adequate quality by the treating team. All required physical examinations, laboratory parameters need to be performed at the primary PBTC institution during the dose finding period of the protocol.

3.5 Criteria to Start Treatment

3.5.1 Subjects must start therapy within seven (7) working days of enrollment.

3.5.2 Laboratory values used to assess eligibility must be no older than seven (7) days prior to the start of therapy. Laboratory tests used to determine eligibility need not be repeated if therapy starts within seven (7) days. If a test that is repeated after enrollment and prior to the start of therapy is outside the limits for eligibility, it must be rechecked 48 hours prior to the start of therapy. If the recheck is still outside the limits for eligibility, the patient may not receive protocol therapy and will be considered off study.

4 REGISTRATION and ENROLLMENT PROCEDURES

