3 PATIENT SELECTION

All subjects must meet the following inclusion and exclusion criteria. No exceptions will be given. Imaging studies to establish eligibility must be done within three weeks prior to enrollment. All other clinical evaluations to establish eligibility must be done within 14 days prior to enrollment.

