3.2.5 Prior Therapy

Stratum I: Less-Heavily Pretreated Stratum

- Patients who have received the following:
 - \leq 4 prior treatment regimens* with either myelosuppressive chemotherapy or biologic agents and/or
 - focal radiotherapy.

Stratum II: Heavily Pretreated Stratum

- Patients who have received ANY one of the following 3 criteria:
 - $>$ 4 prior treatment regimens* with either myelosuppressive chemotherapy or biologic agents and/or
 - craniospinal irradiation and/or
 - myeloablative chemotherapy with autologous stem cell rescue

*A treatment regimen is defined as a single agent (chemotherapeutic or biologic), or a sequential

combination of therapies that can include radiotherapy (with or without concurrent radiosensitizer, chemotherapy, or biologic therapy) followed by maintenance therapy (either single or combination) given over a period of time at either diagnosis or relapse.

Patients must have fully recovered from the acute treatment- related toxicities of all prior therapies prior to entering this study. For those acute baseline adverse events attributable to prior therapy, patients must meet organ function criteria (section 3.2.10) in the Inclusion and Exclusion Criteria.

3.2.5.1 Chemotherapy: Patients must have received their last dose of known myelosuppressive anticancer chemotherapy at least three (3) weeks prior to enrollment in the study or at least six (6) weeks for those receiving nitrosourea.

3.2.5.2 Bone marrow/Stem Cell Infusion:

≥ 3 months since autologous bone marrow/stem cell infusion prior to enrollment (stratum II only)

3.2.5.3 Biologic therapy: Patients should have received their last dose of biologic agent ≥ 7 days prior to enrollment. In the event the patient has received another biologic agent and has experienced ≥ Grade 2 myelosuppression, then at least three (3) weeks must have elapsed prior to enrollment. If the investigational or biologic agent has a prolonged half-life then at least three (3) weeks interval is required. For patients on monoclonal antibodies including Bevacizumab, please refer to list of half-lives available on the PBTC webpage under Generic Forms and Templates.

3.2.5.4 Radiotherapy:

Patients must have had their last fraction of:

- Focal irradiation > 2 weeks prior to enrollment
- Craniospinal irradiation > 3 months prior to enrollment (stratum II only)

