3.2.5.5 Corticosteroids: Patients who are receiving dexamethasone or other corticosteroids must be on a stable or decreasing dose for at least 1 week prior to enrollment. It is recommended that patients be off all steroid therapy or receive the least dose that will control their neurologic symptoms

3.2.5.6 Growth factors: All colony forming growth factor(s) have been discontinued for at least one week prior to enrollment (filgrastim, sargramostim, and erythropoietin). For patients on long acting growth factors, the interval should be two weeks.

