3.2.10 Organ Function

Patients must have normal organ and marrow function as defined below:

- Absolute neutrophil count $\geq 1,000/\text{mm}^3$
- Platelets $\geq 100,000/\text{mm}^3$ transfusion independent (no platelet transfusion one week prior to enrollment)
- Hemoglobin $\geq 8\text{g/dl}$
- Total bilirubin ≤ 1.5 times upper limit of institutional normal (ULN) for age
- AST (SGOT)/ALT(SGPT) ≤ 3 x institutional upper limit of normal for age
- Serum albumin $\geq 3\text{g/dL}$
- Creatinine clearance or radioisotope GFR $\geq 70 \text{ mL/min/1.73 m}^2$ or a serum creatinine based on age/gender as follows:

Serum Creatinine for age/gender		
Age	Maximum Serum Creatinine (mg/dL)	
	Male	Female
1 to < 2 years	0.6	0.6
2 to < 6 years	0.8	0.8
6 to < 10 years	1	1
10 to < 13 years	1.2	1.2
13 to < 16 years	1.5	1.4
≥ 16 years	1.7	1.4

The threshold creatinine values in this Table were derived from the Schwartz formula for estimating GFR (Schwartz et al. J. Peds, 106:522, 1985) utilizing child length and stature data published by the CDC.

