5.2.1 The following are Dose-Limiting Toxicities (DLT's)

- A PD-0332991 (IBRANCE) related adverse event will be considered dose-limiting if it leads to a dose reduction or permanent cessation of treatment during the first course of therapy. All dose modifications in all courses are to follow the guidelines provided in section 6.2.

- Inability to receive the next cycle of PD-0332991 (IBRANCE) within two weeks of the last dose because of lack of hematologic recovery or persisting non-hematologic toxicity.

5.2.1.1 Non-hematologic dose limiting toxicity is defined as:

- Any grade 4 non-hematologic toxicity
- Any grade 3 non-hematologic toxicity with the exception of:
 - Grade 3 nausea and vomiting of < 5 days
 - Grade 3 diarrhea and/or electrolyte disturbances which have not been maximally treated
 - Grade 3 AST/ALT elevation that returns to levels meeting eligibility criteria within 7 days of study drug interruption and does not recur upon restarting drug.
- Any Grade 2 non-hematologic toxicity that persists for > 7 days and is considered medically significant or sufficiently intolerable by patients requires treatment interruption.

5.2.1.2 Hematologic dose limiting toxicity is defined as:

- Grade 3 neutropenia with fever and sepsis
- Any Grade 4 hematologic toxicity with the exception of lymphopenia
- Grade 3 thrombocytopenia and/or requiring a platelet transfusion on 2 separate days within a 7-day period

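### The growth-factor-free interval is counted back from enrollment rather than from the qualifying CBC, so occasionally a patient can qualify on a supported ANC and the unsupported ANC need not be measured before first dose

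*Combined protocol and SAP*

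**What the plan says.** **Support-free intervals (anchored to enrollment).** Section 3.2.5.6: "All colony forming growth factor(s) have been discontinued for at least one week prior to enrollment". The agents named there are filgrastim, sargramostim and erythropoietin. It continues: "For patients on long acting growth factors, the interval should be two weeks". Section 3.2.10 asks for platelets of at least 100,000/mm³, "transfusion independent (no platelet transfusion one week prior to enrollment". The ANC limit of 1,000/mm³ in the same list carries no comparable qualifier.

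**Qualifying laboratory tests (anchored to first dose).** Section 3: "All other clinical evaluations to establish eligibility must be done within 14 days prior to enrollment". Section 3.5.2 narrows this for laboratory values, which may be at most 7 days old when therapy starts, and adds: "Laboratory tests used to determine eligibility need not be repeated if therapy starts within seven (7) days". A recheck rule follows, with this condition: "If a test that is repeated after enrollment and prior to the start of therapy is outside the limits for eligibility". If the recheck also fails, the patient may not be treated.

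**Study calendar (section 10).** The Course 1 CBC cell says weekly and carries footnote A only. Footnote B, the 48-hour rule, is attached in the CBC row only to Courses 2-26. In the Course 1 column it is attached to the pregnancy test.

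**The concern.** The support-free interval is there so that the count used for eligibility reflects unaided marrow function. It does that only if it ends at or before the blood draw. Here it ends at enrollment, and the draw may come earlier.

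Any 7-day laboratory window allows some drift, but a fall after growth factor is withdrawn is predictable in direction. A patient whose unaided ANC is below the 3.2.10 limit could start a drug whose main toxicity is myelosuppression. That patient could then have a DLT that says little about the dose. Two routes exist, if the event is judged at least possibly related:
- section 5.2.1.2, "Any Grade 4 hematologic toxicity with the exception of lymphopenia";
- section 5.2.1, failure to recover counts in time for the next course, where section 5.3 applies the same 3.2.10 limits again.

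Stratum I is closed, so this matters for Stratum II, the heavily pretreated group. Under section 13.2, rejecting dose level 1 suspends accrual to the stratum. Section 5.1.2 says capsule sizes allow no level below 50 mg/m².

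**Working it through.** The plan states no figure to reproduce. The check is on dates, followed by an illustration of consequence.

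**1. Dates.** Let enrollment be Day 0, last short-acting support Day −s (s ≥ 7, section 3.2.5.6), qualifying CBC Day −c (c ≥ 0) and first dose Day t (t ≥ 0). Section 3.5.2 requires c + t ≤ 7.

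- Support-to-CBC gap = s − c. It is smallest at s = 7 and c = 7 − t, giving a gap of t days.
- With t = 0: last G-CSF on Day −7, CBC later that day, enrollment and first dose on Day 0. The gap is 0 days and every timing rule is met.
- A gap below 7 days needs c ≥ 1 and s ≤ 13, so the short gaps run from 0 to 6 days. At t = 7 the minimum gap is 7 and the problem disappears.
- Long-acting product (s ≥ 14): the minimum gap is 14 − (7 − t) = 7 + t, so the short gaps run from 7 to 13 days.
- Support-to-first-dose interval = s + t, at least 7 days (14 for long-acting).

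Take first dose 0 to 7 days after enrollment, and the CBC on any day from 7 days before first dose up to enrollment. That gives 1 + 2 + … + 8 = 36 date pairs. In 8 the CBC falls on enrollment day. In the other 28, support on the latest permitted day leaves too short a gap. If the interval is counted to the CBC, none of the 36 does.

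**2. Consequence (illustration; all DLT risks are assumed).** Section 13.2 rejects a level at two DLTs. For a first group followed by a second:

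P(reject) = P(≥2 in first) + P(exactly 1 in first) × P(≥1 in second).

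*Three then three, base risk 15%.* P(≥2 of 3) = 0.0608, P(1 of 3) = 0.3251 and P(≥1 of 3) = 0.3859. So 0.0608 + 0.3251 × 0.3859 = 0.186. One affected patient, averaged over the two groups:

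| Affected patient's risk | In first three | In second three | Average |
|---|---|---|---|
| 30% | 0.0990 + 0.3953 × 0.3859 = 0.252 | 0.0608 + 0.3251 × 0.4943 = 0.221 | 0.236 |
| 50% | 0.1500 + 0.4888 × 0.3859 = 0.339 | 0.0608 + 0.3251 × 0.6388 = 0.268 | 0.304 |

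With a 10% base the change is from 9% to 15-20%; with a 20% base, from 29% to 33-40%.

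*Current Stratum II cohort.* Section 13.3 reports four patients already enrolled at 50 mg/m², so an amendment can reach only the last two slots. Their DLT outcomes are not given; all four are treated as evaluable at the base risk. P(≥2 of 4) = 0.1095 and P(1 of 4) = 0.3685.
- No affected patient: 0.1095 + 0.3685 × (1 − 0.85²) = 0.212.
- One of the last two at 30%: 0.1095 + 0.3685 × (1 − 0.85 × 0.70) = 0.259.
- One of the last two at 50%: 0.1095 + 0.3685 × (1 − 0.85 × 0.50) = 0.321.

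**3. Weighting by frequency.** Assume one cohort in ten holds an affected patient.
- Three then three: 0.1 × (23.6 − 18.6) = 0.5 points, to 0.1 × (30.4 − 18.6) = 1.2 points.
- Current cohort, if the affected patient is equally likely in any of the six slots (2/6 are reachable): 0.1 × 1/3 × 4.7 = 0.16 points, to 0.1 × 1/3 × 11.0 = 0.37 points.

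**The case against.** **Other rules make the case unusual.** Section 3.2.5 requires 3 weeks from myelosuppressive chemotherapy (6 for nitrosourea) and says "Patients must have fully recovered from the acute" toxicities of prior therapy. This largely stands. It does not exclude the case: growth factor given up to 21 − 7 = 14 days after the last chemotherapy dose satisfies both the 3-week and the 1-week rules, and a supported count can make recovery look complete.

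**Platelets are largely covered.** The 3.2.10 wording calls for transfusion independence, and a count drawn days after a transfusion is hard to certify that way. This stands. What remains is that the bracketed definition runs to enrollment rather than to the count.

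**Footnote B could be read as a 48-hour rule before first dose.** It mentions the start of protocol therapy, but the Course 1 CBC cell does not carry it, and 3.5.2 expressly waives the repeat. Even on that reading, same-day enrollment and dosing with s = 7 and c = 2 leaves a gap of only 5 days.

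**A Day 1 count is likely in practice.** Pharmacokinetic sampling already requires a pre-dose draw, and a CBC repeated after enrollment would bring the recheck rule into play. That is plausible, but it depends on the site's choice.

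**The documents do not say how long a count stays supported.** True. The yardstick here is the plan's own choice of 7 and 14 days.

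**Stronger readings to avoid.** A reader might infer that patients may be dosed while still supported. The dates rule that out in the plan's own terms, since first dose is at least 7 or 14 days after support. A reader might also take 28 of 36 as a patient frequency; it counts possible date pairs only. Averaging the affected patient over all six slots of the current cohort would overstate what an amendment can change.

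**Conclusion.** The point holds, mainly for ANC, as an optional improvement. The interval has the wrong anchor: the qualifying ANC can be drawn 0 to 6 days after short-acting myeloid growth factor, or 7 to 13 days after a long-acting product, and no unsupported value is required before first dose. For platelets it is a clarification.

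The effect is small. One affected patient cannot reject a level alone, because a second DLT is needed. If dose level 1 were rejected, section 13.2 has the stratum reconsidered for amendment or closure, so the DLTs could be looked at again. The conditional increases rest on assumed DLT risks. The average effect, about one percentage point or less, also rests on an assumed frequency of one cohort in ten. The documents do not support a claim that the Stratum I MTD or the Stratum II data so far are distorted.

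**What to change.** - **Section 3.2.5.6:** require the qualifying ANC to be drawn at least 7 days after the last short-acting myeloid growth factor (filgrastim, sargramostim) and at least 14 days after a long-acting one. Leave the erythropoietin rule as it is, because nothing in the documents ties it to ANC or platelets.
- **Section 3.2.10:** state that the qualifying platelet count must be drawn at least 7 days after the last platelet transfusion.

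The cost is one clause in each section at the next amendment, plus an occasional repeat CBC, a few days' delay, or a patient found ineligible. Patients without recent support are unaffected.

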4.1 CTEP Investigator Registration Procedures

Food and Drug Administration (FDA) regulations and National Cancer Institute (NCI) policy require all individuals contributing to NCI-sponsored trials to register and to renew their registration annually. To register, all individuals must obtain a Cancer Therapy Evaluation Program (CTEP) Identity and Access Management (IAM) account (<https://ctepcore.nci.nih.gov/iam>). In addition, persons with a registration type of Investigator (IVR), Non-Physician Investigator (NPIVR), or Associate Plus (AP) (i.e., clinical site staff requiring write access to OPEN, RAVE, or acting as a primary site contact) must complete their annual registration using CTEP's web-based Registration and Credential Repository (RCR) (<https://ctepcore.nci.nih.gov/rcr>). Documentation requirements per registration type are outlined in the table below.

Documentation Required	IVR	NPIVR	AP	A
FDA Form 1572	✓	✓		
Financial Disclosure Form	✓	✓	✓	
NCI Biosketch (education, training, employment, license, and certification)	✓	✓	✓	
HSP/GCP training	✓	✓	✓	
Agent Shipment Form (if applicable)	✓			
CV (optional)	✓	✓	✓	

An active CTEP-IAM user account and appropriate RCR registration is required to access all CTEP and CTSU (Cancer Trials Support Unit) websites and applications. In addition, IVRs and NPIVRs must list all clinical practice sites and IRBs covering their practice sites on the FDA Form 1572 in RCR to allow the following:

- Added to a site roster
- Assigned the treating, credit, consenting, or drug shipment (IVR only) tasks in OPEN
- Act as the site-protocol PI on the IRB approval

Additional information can be found on the CTEP website at https://ctep.cancer.gov/investigatorResources/investigator_registration_packet.htm. For questions, please contact the RCR **Help Desk** by email at <[contact]>.

4.2 CTSU Registration Procedures

This study is supported by the NCI Cancer Trials Support Unit (CTSU).

IRB Approval:

Each investigator or group of investigators at a clinical site must obtain IRB approval for this protocol and submit IRB approval and supporting documentation to the CTSU Regulatory Office before they can be approved to enroll patients. Assignment of site registration status in the CTSU Regulatory Support System (RSS) uses extensive data to make a determination of whether a site has fulfilled all regulatory criteria including but not limited to the following:

- An active Federal Wide Assurance (FWA) number
- An active roster affiliation with the Lead Network or a participating organization
- A valid IRB approval
- Compliance with all protocol specific requirements.

In addition, the site-protocol Principal Investigator (PI) must meet the following criteria:

- Active registration status
- The IRB number of the site IRB of record listed on their Form FDA 1572
- An active status on a participating roster at the registering site.

Requirements for PBTC-042 Site Registration:

- IRB approval (local IRB documentation, a CTSU IRB Certification Form, Protocol of Human Subjects Assurance Identification/IRB Certification/Declaration of Exemption Form, or combination is accepted)

Downloading Site Registration Documents:

Site registration forms may be downloaded directly from the CTSU website.

- Go to <https://www.ctsuo.org> and log in to the members' area using your CTEP-IAM username and password
- Click on the Regulatory tab, followed by the Home tab
- Scroll down to "printable CTSU Forms"
- Select and download 2 forms: CTSU IRB Transmittal and CTSU IRB Certification

Requirements for PBTC-042 Site Registration:

- CTSU IRB Certification
- CTSU IRB/Regulatory Approval Transmittal Sheet (Optional)

Checking Your Site's Registration Status:

Check the status of your site's registration packets by querying the RSS site registration status page of the members' section of the CTSU website. (Note: Sites will be notified by the PBTC when all required documents are uploaded to the CTSU Regulatory Office.)

- Go to <https://www.ctsuo.org> and log in to the members' area using your CTEP-IAM username and password
- Click on the Regulatory tab at the top of your screen
- Click on the Site Registration tab
- Enter your 5-character CTEP Institution Code and click on Go

Note: The status given only reflects compliance with IRB documentation and institutional compliance with protocol-specific requirements as outlined by the Lead Network. It does not reflect compliance with protocol requirements for individuals participating on the protocol or the enrolling investigator's status with the NCI or their affiliated networks.

4.3 Enrollment Procedures

Screening and patient enrollment will be facilitated using the Oncology Patient Enrollment Network (OPEN). OPEN is a web-based registration system available on a 24/7 basis. To access OPEN, the site user must have an active CTEP-IAM account (check at <<https://ctepcore.nci.nih.gov/iam>>) and a 'Registrar' role on either the LPO or participating organization roster. Registrars must hold a minimum of an AP registration type.

All site staff will use OPEN to enroll patients to this study. It is integrated with the CTSU Enterprise System for regulatory and roster data and, upon enrollment, initializes the patient in the Rave database. OPEN can be accessed at <https://open.ctsu.org> or from the OPEN tab on the CTSU members' side of the website at <https://www.ctsu.org>. To assign an IVR or NPIVR as the treating, crediting, consenting, drug shipment (IVR only), or investigator receiving a transfer in OPEN, the IVR or NPIVR must list on their Form FDA 1572 in RCR the IRB number used on the site's IRB approval.

Patient enrollment for this study will be facilitated using the Slot-Reservation System in conjunction with the Registration system in the Oncology Patient Enrollment Network (OPEN). Prior to discussing protocol entry with the patient, all site staff must use the CTSU OPEN Slot Reservation System to ensure that a slot on the protocol is available to the patient. Once a slot-reservation confirmation is obtained, site staff may then proceed to enroll the patient to this study.

Prior to accessing OPEN, site staff should verify the following:

- All eligibility criteria have been met within the protocol stated timeframes.
- All patients have signed an appropriate consent form and HIPAA authorization form (if applicable).

Note: The OPEN system will provide the site with a printable confirmation of registration and treatment information. Please print this confirmation for your records.

Patients with DIPG, Medulloblastoma, or ATRT

For patients with DIPG, Medulloblastoma, or ATRT who are not being screened, reservations may also be made through the CTSU OPEN Slot Reservation system providing time to assess the patient's eligibility. Once a slot reservation confirmation is obtained, site staff may then proceed to enroll the patient on this study. Non screening reservations will be held for a maximum of 10 days. The patient's reservation should be canceled as soon as it is determined that the patient is not eligible or that the family/patient has decided not to consent to the trial.

Patients with all other CNS tumors

All patients with recurrent, progressive or refractory CNS Tumors **except DIPG, medulloblastoma, or ATRT**, must be screened prior to enrollment. Patients must sign the

screening consent to send the pre-trial tumor tissue to **BTRC Tissue Bank** at the University of California, San Francisco for Rb1 testing (see Section 9.1.1 for requirement) and have their Rb1 status confirmed prior to enrolling in the PBTC-042 study. Only patients who are Rb1 positive will be eligible to enroll.

